1. METHODOLOGY

The purpose of this statistical analysis plan is to provide detailed information on the statistical analysis of the data of study P13-990. The plan is based on the final protocol, incorporating administrative change 1, dated 17 December 2015.

1.1 *Introduction*

Ankylosing spondylitis (AS) and psoriatic arthritis (PsA) are both associated with often debilitating clinical symptoms, reduced functional impairment and significant impact on quality of life. As a consequence both diseases imply a significant economic burden, arising from both the direct costs of medical and disability. Health economics data becomes increasingly important to justify the costs of medicines.

Very limited data are available about the employment status and the work productivity of patients with AS and PsA in Belgium. The same is true for the impact of adalimumab treatment on employment status and work productivity.

The aim of this study is to analyse the employment status and work productivity of patients with AS and PsA before and after the start of adalimumab and to look at the relationship between employment status, work productivity, disease activity and clinical evaluations.

1.2 *Study Objectives and Endpoints*

1.2.1 *Study Objectives*

The main objective of the study is to observe in daily practice the evolution of work productivity over 18 months in AS and PsA patients after the start of adalimumab treatment.

The following questions were addressed:

- What is the employment status of AS and PsA patients with active disease before initiation of adalimumab?
- In the patients who work at baseline, what is their work productivity?
- Does adalimumab therapy enable people with AS and PsA to return to work or work more productively?

The secondary objectives are to:

- Investigate if there is a difference in evolution of employment status and work productivity after initiation of adalimumab treatment between AS and PsA patients throughout the study
- Investigate the relationship between disease activity and employment situation and the relationship between clinical evaluations and employment situation at baseline and after 18 months
- Investigate possible correlations between disease activity and work productivity and between clinical evaluations and work productivity

1.2.2 *Study Endpoints*

The primary endpoints is Total Work Productivity Impairment (TWPI) due to AS/PsA:

18 months versus baseline in all patients, measured by the WPAI-SHP questionnaire.

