1.4 Sample Size Justification

The main objective of this study is to observe the working status in AS and PsA patients before and after the start of adalimumab therapy in daily practice. The primary variable is the change in total work productivity impairment (TWPI) due to AS/PsA between baseline and Month 18. The change will be evaluated in a descriptive way by means of the mean change observed in the study and its 95% confidence interval.

The number of patients to be enrolled (200) was determined on the basis of the recruiting capacity of the participating investigational sites during the foreseen recruitment period of 12 months.

Based on data from Reilly et al¹ it is estimated that about 65% of the patients of the study population are working and therefore evaluable for work productivity impairment.

Supposing that 80% of the employed patients have data available over an 18 month period, the mean change in TWPI will be estimated on the basis of data for about 100 patients.

Based on data for a 16 week treatment period it is estimated that the standard deviation of the change in TWPI will be about 23.8. Since the estimate to be made is for an 18 month treatment period, 95% confidence intervals are also calculated for a somewhat more important standard deviation, arbitrarily set equal to 30.0.

¹ Reilly MC, Zbrozek AS, Dukes EM. The validity and reproducibility of a work productivity and activity impairment instrument. *Pharmacoeconomics*. 1993; 4: 353–65.

The table below contains 95% confidence intervals on the mean change for some possible mean changes (-10.0, -15.0 and -20.0), and for standard deviations (SD) of 23.8 and 30.0, supposing data will be available for 100 patients:

Mean change	SD	95% CI
-10.0	23.8	[-14.7 ; -5.3]
-15.0	23.8	[-19.7 ; -10.3]
-20.0	23.8	[-24.7 ; -15.3]
-10.0	30.0	[-16.0 ; -4.0]
-15.0	30.0	[-21.0 ; -9.0]
-20.0	30.0	[-26.0 ; -14.0]

These intervals show that quite precise estimates can be obtained of the change in TWPI on the basis of the planned sample size.

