1.9 Data Handling

The following data handling transformations are performed for the analysis:

Onset data

- Date of enrolment is taken to be date of informed consent

WPAI Questionnaire

- For patients with (number of hours missed due to psoriasis = number of hours worked = 0), Absenteeism, Presenteeism and Total work productivity impairment are set to missing.
- If the answer to Question 1 of the WPAI Questionnaire is not YES but there is an answer to any of Questions 2, 3, 4, or 5, then the answers to these questions are considered to be missing.

Serious Adverse Events

In case of a partial or missing date for the start of a serious adverse event it will be

assumed that the event was study-emergent unless it can be determined from the partial start or stop date that the event definitely started before the date of informed consent or more than 70 days after the last administration of study medication.

Last Observation and Last Attended Visit

The analysis of individual scales is performed for each visit and for the last observation after baseline. For multi-item questionnaires the last observation after baseline is defined as the observation for the last visit after baseline at which any of the items of the questionnaire is completed.

The analysis of the relation between variables is performed for data recorded at baseline, at Month 18, and at the last attended visit.

Other Missing Data

No other estimation will be performed of missing data. In order to obtain estimates for the end of the study, use is made of the last observation after baseline. If date of completion/withdrawal was missing it has been set to date of last contact.

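### SAP 1.9 relies on the last observation for end-of-study TWPI despite known dropout; rank it as supportive and add a repeated-measures sensitivity estimate of the Month 18 change

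*SAP*

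**What the plan says.** SAP 1.2.2 gives the primary endpoint as TWPI, "18 months versus baseline in all patients, measured by the WPAI-SHP questionnaire". SAP 1.4 agrees: "The primary variable is the change in total work productivity impairment (TWPI) due to AS/PsA between baseline and Month 18", to be described by its mean and 95% CI. Protocol 10.2.1 names the same variable.

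On missing data, SAP 1.9 says "No other estimation will be performed of missing data" and then "In order to obtain estimates for the end of the study, use is made of the last observation after baseline". SAP 1.10 explains that last-observation analyses were *also* decided on because a sizeable share of patients had left before Month 18. SAP 5.1 lists the TWPI change to each visit and to the last observation, without ranking them.

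Other rules in SAP 1.9 decide who has a TWPI. For a multi-item questionnaire the last observation is taken from "the last visit after baseline at which any of the items of the questionnaire is completed". "If the answer to Question 1 of the WPAI Questionnaire is not YES", any answers to Q2 to Q5 are treated as missing. If no hours were worked and none were missed for disease (Q2 = Q4 = 0), "Absenteeism, Presenteeism and Total work productivity impairment are set to missing".

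**The concern.** Dropout was known to matter when the SAP was written, and the only device offered against it is the last observation. That value comes from an earlier visit. It estimates the Month 18 mean only if TWPI would not have changed after the patient left. If TWPI improves gradually, or if patients leave after a bad visit, the last-observation mean understates the improvement. If benefit wanes, it can overstate it. The intermediate visits are described and supply last observations, but nothing uses them to estimate Month 18.

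TWPI also exists only for people in work. The study asks "Does adalimumab therapy enable people with AS and PsA to return to work or work more productively", yet a baseline worker who has stopped working contributes to neither TWPI change at Month 18. A reader of the TWPI table should see how many such patients there are.

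**Working it through.** **1. The plan's own precision.** Inputs from SAP 1.4: 200 enrolled, 65% working, 80% of those with 18-month data, SD 23.8 or 30.0. Workers: 200 × 0.65 = 130. Evaluable: 130 × 0.80 = 104, which the SAP rounds to about 100. Half-width = t(0.975; 99) × SD/√100 = 1.984 × 23.8/10 = 4.72, and 1.984 × 30/10 = 5.95. All six intervals in the SAP table reproduce.

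**2. The mechanism, by arithmetic.** The documents give no trajectory or dropout rate, so these are assumptions. Let 40% leave at random, a third each after Months 3, 6 and 12. A positive bias means that improvement is understated.
- Gradual improvement, changes −4, −8, −12, −15: last-observation mean = 0.60 × (−15) + (0.40/3) × (−4 − 8 − 12) = −9.0 − 3.2 = −12.2. The truth is −15, so the bias is +2.8.
- Waning benefit, changes −18, −17, −13, −10: 0.60 × (−10) + (0.40/3) × (−18 − 17 − 13) = −6.0 − 6.4 = −12.4. The truth is −10, so the bias is −2.4.
- Plateau at −15 throughout: no bias.

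**3. Other dropout mechanisms, by simulation.** Assumptions: 130 workers, baseline mean 50, SD 25, correlation between visits 0.575 falling to 0.45, SD of change 24.2 to 26.3. The three trajectories above were crossed with 20, 30 or 40% dropout, three mechanisms, and values unbounded or clipped to 0–100 (54 scenarios, 500 studies each). Dropout on TWPI was logistic with slope 0.04 per point. The model was maximum likelihood with unstructured covariance. Bias in points:

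| Dropout depends on | Last observation | Observed Month 18 | Repeated-measures model |
|---|---|---|---|
| nothing (random) | −2.3 to +2.8 | within 0.4 | within 0.4 |
| observed TWPI | +0.8 to +6.7 | −0.1 to +0.5 | −0.2 to +0.2 |
| the next, unseen TWPI | −3.7 to +2.1 | −2.2 to −0.8 | −3.6 to −1.5 |

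A separate run with dropout on observed TWPI gave about +0.5 to +6.4 for the last observation, +0.2 to +1.5 for observed Month 18, and about 0 for the model. In the 54 scenarios the last observation minus observed Month 18 ran from −2.6 to +6.6. The median absolute gap was 1.5. It was under 1 point in 20 scenarios and reached 4.7 in 3, all with gradual improvement and dropout after poor values.

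**4. Who has no TWPI.** The SAP 1.6 formula needs Q2, Q4 and Q5. Take a constructed baseline worker:
- Baseline, Q2 = 8, Q4 = 32, Q5 = 5: 100 × 8/40 + 100 × (32/40) × 0.5 = 60.
- Month 3 (4, 36, 3): 10 + 27 = 37.
- Month 6 (8, 32, 6): 20 + 48 = 68.
- Month 12: Q1 = NO and Q6 answered.

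Month 12 is the last visit with any item completed, so it is selected, and TWPI there is missing. Using the last available TWPI instead moved the mean by only 0.0 to +0.6 points in 12 simulated scenarios with about 5 or 10 of 130 stopping work. The visit rule is therefore nearly immaterial. Q2 = Q4 = 0 in an assumed 2–8% of 104 workers loses 2 to 8 patients and widens the half-width by at most 0.3.

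**5. Scoring job loss as 100%.** Suppose the other workers change by −15 and each loss adds +50. Five losses give (125 × −15 + 5 × 50)/130 = −12.5. Ten give (120 × −15 + 10 × 50)/130 = −10.0. Now also score 20 to 40 disease-related baseline non-workers at 100% and let 10 return at 35%. The ten-loss figure becomes (120 × −15 + 10 × 50 − 10 × 65)/(150 to 170) = −13.0 to −11.5. The answer depends on whether returns are counted.

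**The case against.** The case against is strong on three points.

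First, the ranking can be inferred. SAP 1.2.2 and 1.4 name Month 18, SAP 1.10 introduces the last observation as an addition, and SAP 5.1 with 1.7 reports the observed Month 18 change with a 95% CI in any event. A reader might infer from SAP 1.9 that the last observation has replaced the primary result; the documents do not support that.

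Second, job loss is not hidden. SAP 5.1 cross-tabulates professional activity by baseline activity, section 4 lists patients whose employment changed, and SAP 1.5 records whether several non-working states are due to disease. TWPI is by definition a measure among workers. A reader might infer that the any-item rule distorts the mean, or that the TWPI mean must flatter the work outcome. Step 4 shows the rule hardly matters, and the documents do not give the direction or size of any effect of job loss.

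Third, the model gains little over the observed Month 18 mean when dropout depends on observed TWPI, and did worse than it in all 18 scenarios with dropout on unseen values. The study is descriptive (Protocol 10.3.2), so no error rate is at stake.

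All this stands, and it limits the point. It does not rescue the last observation as the sole device for dropout. That was further from the truth than observed Month 18 in all 18 scenarios with dropout on observed TWPI, in all 12 random-dropout scenarios with a changing trajectory, and in 11 of 18 with dropout on unseen values.

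**Conclusion.** The concern holds as a cheap improvement to the handling of dropout, not as a flaw in the endpoint. The last observation is a poor substitute for Month 18 when TWPI is still changing or dropout follows poor values. The bias is about +0.5 to +6.4 points in assumed scenarios with dropout on observed TWPI, so at its largest it exceeds both planned half-widths; in most scenarios it is modest. A likelihood estimate is close to unbiased in those scenarios. It is not protection against dropout on unseen values, where none of the three estimates is dependable. All sizes rest on assumed trajectories, dropout rates and correlations, because the documents supply none. The missing labels and counts are matters of clarity.

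**What to change.** 1. In SAP 1.9 and 5.1, state that the observed baseline-to-Month 18 TWPI change with its 95% CI is the primary result and that the last observation is supportive.
2. Add a sensitivity analysis for dropout: a likelihood repeated-measures model of TWPI at baseline and Months 3, 6, 12 and 18 in patients with a baseline TWPI, with visit as a category and unstructured covariance, reporting the Month 18 minus baseline contrast with 95% CI. State that it assumes dropout depends on observed data, that it can do worse than the observed mean otherwise, and that it predicts TWPI for people who stopped working as if they still worked.
3. Beside the TWPI change, show the number of baseline workers with Q1 = NO (already available from the SAP 5.1 cross-tabulation) and the number with Q2 = Q4 = 0 (not now reported).
4. Optional only: a table scoring disease-related job loss as 100% impaired, labelled a convention and shown beside returns to work. The status list in SAP 1.5 has no sick-leave or disability category, so such losses may be incompletely identified.
5. List the additions in SAP 1.10 as made after dropout was known.

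The cost is a few sentences, two counts and one standard SAS procedure on data already collected.

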1.10 Changes from the Analysis Foreseen in the Protocol

For the DLQI the protocol only foresaw an analysis of the total score and the categories. In order to provide additional information descriptions will also be provided for the 6 scales of the DLQI, and for the regrouped categories ≤ 5 and > 5 .

The protocol foresaw to analyse the evolution of the work productivity data, the health-related quality of life scores, and the disease activity measures and clinical evaluations based upon the data collected in time windows around the foreseen study visits. Since data were collected in the CRF around the planned visits, it was decided to analyse the data by reported study visit.

Since an important proportion of patients dropped out before the Month 18 visit it was decided also to perform analyses for the last observation after baseline.

The protocol did not foresee to perform an analysis of the safety data. It was decided to perform an analysis of adverse events and of the course of the study and for this purpose a safety analysis set was defined.

In order to better comprehend the effect of employment status it was decided to provide frequencies of extra-articular disease manifestations broken down by employment status.

The protocol foresaw to primarily perform the analysis on the basis of the PPS and to perform a sensitivity analysis of the TWPI on the ITT Set. It was decided only to perform the latter analysis in case the difference between the two analysis sets exceeds 10% of the patients of the PPS.

2. SAMPLE DESCRIPTION

2.1 Study Population

- Number of patients in the ITT Set and the PPS, and number of patients in the ITT Set and the PPS broken down by indication.

2.2 Study Period

For all patients enrolled:

- Date of first and last inclusion, data of last study completion/withdrawal.

3. ONSET DATA

The analysis is performed for all patients and broken down by indication.

3.1 Demographic Data

- Descriptive statistics for age.
- Frequency distribution for gender and ethnic origin.

3.2 Medical Data

- Frequency distribution for indication for adalimumab therapy.
- Frequency distribution for each extra-articular disease manifestation (psoriasis, inflammatory bowel disease, uveitis).
- Frequency distribution for combinations of extra-articular disease manifestations.
- Frequency distribution for combinations of extra-articular disease manifestations broken down by employment status.
- Frequency distribution for combinations of currently active extra-articular disease manifestations.
- Frequency distribution for combinations of currently active extra-articular disease manifestations broken down by employment status.
- Frequency distribution for smoking status.
- Frequency distribution for each type of other medical history (cardiovascular diseases, cardiovascular risk factors, diabetes, renal disease, hepatic disease, lung disease, mental disorders, other).
- List of items of other medical history.
- Frequency distribution for each type of medication (analgesic, NSAID, DMARD, steroid, biologic therapy).
- Frequency distribution for combinations of types of medication.

3.3 Educational Background and Employment Situation

- Frequency distribution for highest educational level achieved.
- Frequency distribution for current employment status.
- For housewife/houseman, unemployed, retired, part-time employed, frequency distribution for whether it is due to the disease.
- Frequency distribution for current job content.
- Frequency distribution for current occupational situation.

4. COURSE OF THE STUDY

The analysis is performed for all patients and broken down by indication.

Study duration and study termination

- Descriptive statistics for study duration.
- Frequency distribution for reason for study termination.

Adalimumab treatment

- Descriptive statistics for treatment duration.
- Frequency distribution of any change in adalimumab treatment.
- For the patients for whom any change in adalimumab treatment was recorded, list of the data recorded concerning adalimumab treatment.

Concomitant Medications

- Frequency distribution of subjects taking other AS/PsA medication by WHO-DRUG anatomical class.
- Frequency distribution of subjects taking other AS/PsA medication by WHO-DRUG anatomical and therapeutic class.

Employment Situation

- Frequency distribution of any change in employment situation.
- For the patients for whom any change in employment situation was recorded, list of the data recorded at each visit concerning employment situation.

5. EFFICACY DATA

5.1 WPAI Questionnaire

- Frequency distribution of professional activity at baseline, at each visit, and at the last observation.
- Frequency distribution of professional activity at each visit and at the last observation, broken down by professional activity at baseline.

For absenteeism, presenteeism, TWPI, and percentage activity impairment:

- Descriptive statistics at baseline, at each visit, and at the last observation.
- Descriptive statistics of the change between baseline and each visit, and between baseline and the last observation.

5.2 DAS28 (PsA)

- Descriptive statistics of the DAS28 score at baseline, at each visit, and at the last observation.
- Descriptive statistics of the change in DAS28 score between baseline and each visit, and between baseline and the last observation.

5.3 BSA (PsA)

- Descriptive statistics of BSA at baseline, at each visit, and at the last observation.
- Descriptive statistics of the change in BSA between baseline and each visit, and between baseline and the last observation.

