1.5 Study Data Considered for the Analysis

The following data are used for the analysis:

Data only collected at screening (baseline)

- Date of inclusion (screening) and date informed consent form was signed
- Demographic data
 - Year of birth
 - Gender
 - Ethnic origin (Caucasian, Hispanic, Black, Asian, Other).
- Indication for adalimumab therapy (ankylosing spondylitis, psoriatic arthritis) and year of diagnosis.
- Extra-articular disease manifestations: None or
 - Psoriasis
 - Inflammatory bowel disease
 - Uveitis
For each manifestation: Yes/no and (currently active, currently inactive)
- Smoking status (never smoked, ex-smoker, smoker, unknown)
- Other medical history: None or
 - Cardiovascular diseases
 - Cardiovascular risk factors
 - Diabetes
 - Renal disease
 - Hepatic disease
 - Lung disease
 - Mental disorders
 - Other and specification
- Medication history
 - Analgesics
 - NSAIDs

- DMARDs
- Steroids
- Biologic therapy.
- Education background (highest level achieved): None, primary school, secondary school, higher education (non-university), university.
- Start date adalimumab therapy.

Data collected at each visit

- Date of visit
- Employment situation (to be answered at baseline, and at each follow-up visit in case of any change since the last visit):
 - Current employment status:
 - Housewife/houseman, due to As/PsA (yes, no)
 - Unemployed, due to As/PsA (yes, no)
 - Retired, due to As/PsA (yes, no)
 - Part-time employed: Percentage, due to As/PsA (yes, no)
 - Full-time employed
 - Student.
 - Current job content:
 - Professional or technical
 - Administrative or managerial
 - Sales
 - Service tasks
 - Agricultural
 - Production/manufacturing, transport equipment operator, laborer
 - Armed forces
 - Other and specification.
 - Current occupational situation:
 - Employee
 - Independent
 - Public/civil servant
 - Volunteer
 - Other
- Disease activity measures and clinical evaluations:
 - Only PsA
 - Body Surface Area (BSA) affected (no psoriatic lesions, <3%, 3-10%, 11-20%, >20%).
 - DAS28 score.
 - Only AS
 - BASDAI
 - Consists of 6 items assessed on ordinal scales. Higher scores indicate higher severity. The scores for Items 1 to 5 are integers between 0 and 10. The scores for Item 6 is a continuous assessment between 0 and 10.
 - The total score is calculated as:
[(Item 1+Item 2+Item 3+Item 4)+(Item 5+Item 6)/2]/5

PsA and AS

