1.7 Statistical Methodology

The analysis will consist of data descriptions and statistical hypothesis testing. Throughout this document, the following terminology is used for indicating the type of descriptive analysis to be performed:

- ‘Descriptive statistics’ is used to indicate the description to be provided for quantitative variables, and includes the mean, standard deviation, 95% confidence interval (CI) on the mean, minimum, 1st quartile, median, 3rd quartile, maximum,

- number of available observations, and number of missing observations.
- ‘Frequency distribution’ is used to indicate the description to be provided for categorical variables and consists of numbers and percentages for each of the scores or categories.

For the variables recorded for both AS and PsA patients the descriptions will be given for all patients as well as separately for each subgroup.

The relationship between TWPI and disease activity at baseline and between TWPI and clinical evaluations at baseline will be evaluated by means of the Spearman rank correlation coefficient.

The relationship between work status and disease activity and between work status and clinical evaluations will be evaluated by means of analysis of variance, controlled for indication, if applicable.

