5.6 BASDAI (AS)

- Descriptive statistics of the BASDAI total score at baseline, at each visit, and at the last observation.
- Descriptive statistics of the change in BASDAI total score between baseline and each visit, and between baseline and the last observation.
- Frequency distribution of the BASDAI total score category (axial disease) at baseline, at each visit, and at the last observation.
- Frequency distribution of the BASDAI total score category (axial disease) at each visit and at the last observation, broken down by the BASDAI total score (axial disease) at baseline.

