5.7 HAQ-S (AS)

- Descriptive statistics of the HAQ-S score at baseline, at each visit, and at the last observation.
- Descriptive statistics of the change in the HAQ-S score between baseline and each visit, and between baseline and the last observation.
- Frequency distribution of the possibility of performing daily activities at baseline, at each visit, and at the last observation.
- Frequency distribution of the possibility of performing daily activities at each visit and at the last observation, broken down by the possibility of performing daily activities at baseline.
- Descriptive statistics of the HAQ-S additional items (pain, general health, stiffness) score at baseline, at each visit and at the last observation.
- Descriptive statistics of the change in the HAQ-S additional items between baseline and each visit, and between baseline and the last observation.

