5.10 Relation Between Work Status and Clinical Evaluations

For DAS28 score, BSA, DLQI score, HAQ-DI score, BASDAI total score, HAQ-S (total score and scores for pain during the past week, general health, and stiffness), physician and patient assessments of disease activity, and patient assessment of pain:

- For baseline, Month 18, and the last attended visit:
 - Descriptive statistics broken down by work status (Q1 of the WPAI).
 - Evaluation of the effect of work status (and indication) by means of analysis of variance.
- For the change between baseline and Month 18, and between baseline and the last attended visit, descriptive statistics broken down by work status (Q1 of the WPAI) at baseline.

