5.11 Relation Between Work Productivity and Clinical Evaluations

For baseline, the change between baseline and Month 18, and the change between baseline and the last attended visit, Spearman rank correlation between:

- Absenteeism, presenteeism, TWPI, percentage activity impairment and
- DAS28 score, BSA, DLQI score, HAQ-DI score, BASDAI total score, HAQ-S scores (total score and scores for pain during the past week, general health, and stiffness), physician and patient assessments of disease activity, patient assessment of pain.

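### BSA is recorded in five unequal, open-topped categories, but SAP 5.3 and 5.10 plan means, mean changes and analysis of variance without defining a score

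*SAP*

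**What the plan says.** **Recording.** SAP 1.5 lists the variable for PsA patients as "Body Surface Area (BSA) affected (no psoriatic lesions, <3%, 3-10%, 11-20%, >20"%). These are five ordered classes, and no percentage is listed beside them.

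**Terminology.** SAP 1.7 separates two kinds of summary. Descriptive statistics (mean, SD, 95% CI, range, quartiles) are for quantitative variables. A frequency distribution "is used to indicate the description to be provided for categorical variables and consists of numbers and percentages" for each category.

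**Planned BSA analyses.**
- SAP 5.3 has two items, both descriptive statistics: one for BSA at each time point, and "Descriptive statistics of the change in BSA between baseline and each visit, and between baseline and the last observation".
- SAP 5.10 names BSA alongside the numeric scores. For baseline, Month 18 and the last attended visit it plans descriptive statistics by work status and "Evaluation of the effect of work status (and indication) by means of analysis of variance". It then plans "For the change between baseline and Month 18, and between baseline and the last attended visit, descriptive statistics broken down by work status" at baseline.
- SAP 5.11 includes BSA in the rank correlations: "For baseline, the change between baseline and Month 18, and the change between baseline and the last attended visit, Spearman rank correlation between" the work measures and the clinical measures.

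**Scoring.** SAP 1.6 derives BASDAI, HAQ-DI, HAQ-S, WPAI and DLQI scores and has no entry for BSA. SAP 1.9 gives no BSA coding, and SAP 1.10 declares no departure for it. Protocol 6.5.3 gives no BSA scale either.

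**The concern.** A mean, an SD, a mean change or an analysis of variance needs a number for each category. To run 5.3 and 5.10, a programmer would have to choose those numbers, including one for the open class >20%. Integer codes treat clearing the last <3% of lesions as equal to dropping from >20% to 11-20%. Midpoints do not, but they need an assumed value for the top class.

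The choice can alter the size of the reported change and of the work-status difference, and sometimes the direction. Read literally, 5.3 also produces no count of patients per BSA category, although that is what was recorded and what a reader can interpret. BSA is a named secondary endpoint (protocol 5.4 and 10.2.2, SAP 1.2.2).

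**Working it through.** The documents give no BSA results or assumptions, so there is no planned figure to reproduce. The patient counts and top-class values below are invented, to show what the coding can do.

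**1. Size of one category step.** Midpoints from the SAP 1.5 classes are none = 0, <3% = 1.5, 3-10% = 6.5 and 11-20% = 15.5.

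| Step | Integer codes 0-4 | Midpoints (points) |
|---|---|---|
| none to <3% | 1 | 1.5 - 0 = 1.5 |
| <3% to 3-10% | 1 | 6.5 - 1.5 = 5.0 |
| 3-10% to 11-20% | 1 | 15.5 - 6.5 = 9.0 |
| 11-20% to >20% | 1 | top value - 15.5 |

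The last step is 5.5, 14.5, 24.5, 44.5 or 84.5 points for top values of 21, 30, 40, 60 or 100.

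**2. Mean change (SAP 5.3), top class not used.** Ten patients go from 11-20% to 3-10%, and 20 go from none to <3%.
- Codes: (10 × -1 + 20 × 1)/30 = +0.33 steps. SD 0.959; 95% CI with 29 df: -0.02 to 0.69.
- Midpoints: (10 × -9 + 20 × 1.5)/30 = -2.0 points. SD 5.03; 95% CI: -3.88 to -0.12.

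The same patients show a point estimate of worsening under one coding. Under the other they show an improvement whose interval excludes zero.

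**3. Work-status difference (SAP 5.10), top class not used.** There are 20 employed patients, half with none and half with 11-20%, and 20 not employed, all with 3-10%.
- Codes: 1.5 - 2.0 = -0.5.
- Midpoints: 7.75 - 6.5 = +1.25 points.

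**4. Work-status difference, top class used.** Counts across the five classes are 2, 5, 9, 2, 2 (employed) and 1, 4, 8, 7, 0 (not employed). The employed mean is (5 × 1.5 + 9 × 6.5 + 2 × 15.5 + 2 × top)/20 = (97 + 2 × top)/20. The not-employed mean is (4 × 1.5 + 8 × 6.5 + 7 × 15.5)/20 = 166.5/20 = 8.325.

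| Value given to >20% | Employed mean | Difference |
|---|---|---|
| 21 | 6.95 | -1.375 |
| 30 | 7.85 | -0.475 |
| 40 | 8.85 | +0.525 |
| 60 | 10.85 | +2.525 |

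Only the assumed top value has moved.

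**5. Which BSA results depend on the coding.**
- Medians and quartiles of the level can be read back as categories.
- The baseline Spearman correlation is the same under any strictly increasing code, because the ranks do not change. In simulated data for 50 patients it was -0.142 with integer codes and with midpoints.
- The Spearman correlation of BSA change does depend on the coding, because the size of a difference depends on the spacing. In the same simulation it was 0.562 with integer codes and about 0.52 with midpoints.
- Moving all codes by a constant (0-4 or 1-5) alters the mean level but not changes, differences or the F test. The spacing and the top value are what matter.

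**The case against.** **The general rule may already cover this.** SAP 1.7 gives categorical variables counts and percentages, and protocol 10.3.2 foresees frequencies and percentages for variables with categories. SAP 5.3 follows the same two-line template as 5.2 and 5.5, so a drafting slip is plausible. This explains how 5.3 may have arisen. It does not tell the programmer to override 5.3, and it does not help with the analysis of variance in 5.10.

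**The examples are built to reverse.** This is fair. A mean change can change sign only if patients move in opposite directions across steps of different size. If all movement is one way, every increasing code gives the same sign. The codes interval in the first example includes zero (p = 0.067). The work-status differences lie within noise: p = 0.15 and 0.49 in step 3, and 0.48, 0.84, 0.86 and 0.54 in step 4. They show that an estimate can change sign, not that a significant conclusion would. The dependence of size on coding needs no special pattern.

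**One line stating the codes would suffice.** It would remove the ambiguity, and it is an acceptable minimum. Integer codes would still weight unequal steps equally, and midpoints would still rest on an assumed top value.

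**The precedents are imperfect.** The DLQI and BASDAI categories are cut from numeric scores that are also summarised by means. The HAQ-S daily-activities item is the close match: a directly recorded five-level ordinal item, for which SAP 5.7 plans "Frequency distribution of the possibility of performing daily activities at baseline, at each visit, and at the last observation". SAP 5.10 and 5.11 do not list it.

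**Conclusion.** The concern holds. SAP 5.3 and 5.10 apply quantitative methods to a variable that SAP 1.5 records as ordered categories. This contradicts SAP 1.7, and no score is defined anywhere. The BSA means, SDs, confidence intervals, mean changes, change correlations and analysis of variance are therefore not determined by the plan.

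The midpoint steps differ sixfold (1.5 to 9.0 points) before the open class is considered, and the top step is 5.5 to 84.5 points over top values from 21% to 100%. Sign reversal is possible but not shown to be likely, since it needs mixed movement or mixed distributions.

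The consequence is limited to one secondary measure in PsA patients, in a study the protocol describes as essentially descriptive. It should be corrected, but it does not bear on the primary endpoint. The conclusion assumes that SAP 1.5 describes the recorded data correctly. If the case report form holds a percentage, SAP 1.5 needs correcting instead.

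**What to change.** - **SAP 5.3:** replace both items with frequency distributions of the BSA category at baseline, each visit and the last observation, plus shift tables from the baseline category. This is the layout already used in 5.7 for the HAQ-S item and in 5.6, which plans "Frequency distribution of the BASDAI total score category (axial disease) at baseline, at each visit, and at the last observation".
- **SAP 5.10:** for BSA, give frequency distributions by work status, use shift tables by baseline work status for the change, and replace the analysis of variance with a Wilcoxon rank-sum test or a proportional-odds model.
- **SAP 5.11:** keep the Spearman correlations, but define BSA change as the number of category steps and label it so.
- **If a numeric summary is still wanted:** state the score for each category in 1.6, including the value for >20%, and show results over a range of that value.

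The cost is SAP wording, the BSA table templates in 5.3 and 5.10, and a label in 5.11. No new data are needed. None of this recovers changes within a category, which are lost at recording.
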